- Screening Period: Screening is to be conducted within 60 days prior to randomization; randomization must occur within 6 months of the transplant date. Eligible patients must have undergone HDT and a single ASCT within 12 months of the start of induction treatment and be MRD positive at the time of screening. Adaptive Biotechnologies' next generation sequencing (NGS)-based MRD assay will be used to assess MRD positivity during screening for enrollment and randomization of treatment. Residual bone marrow sample, if available, will be banked for future tests, if required. Note that, if results of post-ASCT NGS assay (ie, Adaptive Biotechnologies' NGS-based MRD assay) conducted previously as part of institutional standards are available at screening, these results are to be recorded in the electronic case report form (eCRF).
- Maintenance Phase: Comprised of up to thirty-six, 28-day cycles. Patients will be randomized to receive maintenance treatment with SC daratumumab in combination with lenalidomide or lenalidomide alone. Study treatment will continue until confirmed progressive disease (PD), unacceptable toxicity, withdrawal from study or the end of study maintenance phase.
- EOT Visit: An EOT visit is to be scheduled 30 days (± 7 days) after the last dose of study treatment(s) or, if a patient begins new therapy for multiple myeloma, as soon as possible prior to the start of next-line therapy.
- Follow-up Phase: After the EOT visit, patients will continue to be followed until the end of the study, every 6 months. The end of the study is defined as 36 months from the date of randomization of last patient.

Planned enrollment includes a total of 214 patients to be randomly allocated in a 1:1 ratio to one of the two treatment arms, with randomization stratified by cytogenetic risk (high versus standard/unknown).

PATIENT POPULATION

Key entry criteria include the following. A patient must:

- 1. Be 18 to 79 years of age,
- 2. Have newly diagnosed multiple myeloma with a history of a minimum of 4 cycles of induction therapy, have received HDT and ASCT within 12 months of the start of induction therapy, and be within 6 months of the date of ASCT at the time of randomization.

- 3. Have a very good partial response or better assessed per the International Myeloma Working Group (IMWG) 2016 criteria at the time of randomization.

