Spirometry test (ie, FEV1) (only in patients with known or suspected COPD or asthma)	x	As clinically indicated	-	-	Spirometry (ie, measurement of FEV1) is required at screening in patients with known or suspected COPD or asthma, unless if performed as part of standard of care anytime from 60 days prior to transplant up to randomization.
ECOG performance status	x	D1 of odd cycles (ie, C1, C3, C5, C7, and so on)	X	-	ECOG performance status assessments should be obtained prior to any other study procedures planned for the same day whenever possible.
12-Lead ECG	Х	As clinically indicated	-	-	-
Physical examination	х	Symptom and disease directed exam as clinically indicated	-	-	During screening, a complete physical examination is to be conducted with measurement of height. Thereafter, only a symptom and disease directed physical examination is required as clinically indicated.
Weight	Х	On C1D1	-	-	-
Vital signs	х	 Lenalidomide only arm: D1 of odd cycles (ie, C1, C3, C5, C7, and so on). Daratumumab + lenalidomide arm: C1D1: Up to 30 minutes before administration; at end of administration; and at 0.5 and 1 hour (+/-5 minutes) after end of administration. C3 onwards: Immediately before and at the end of daratumumab administration on D1 of odd cycles (ie, C3D1 C5D1, C7D1, etc. 	-	-	To include pulse, temperature, and blood pressure measured in a sitting position after approximately 5 minutes of rest

		STUDY PHA			
PROCEDURE	Screening	Maintenance (Cycles 1 – 36)	ЕОТ	FOLLOW-UP (FROM THE DATE OF LAST STUDY TREATMENT UNTIL THE END OF STUDY)	Notes
Blood type/indirect antiglobulin test (all patients)	х	-	-	-	A wallet card with the patient's blood type is to be provided to patients receiving daratumumab.
SAFETY AND LABORATORY ASSESSMENTS (TO BE	CONDUCTED AT	LOCAL LABORATORY)			
Pregnancy test (women of childbearing potential only)	x		€x	÷	 Serum β-hCG pregnancy test: Within 10-14 days before the first dose on C1D1; Within 24 hours before the first dose on C1D1; and Each month thereafter beginning with C2. Serum β-hCG or urine pregnancy test at the EOT visit.
					For patients remaining on lenalidomide after the EOT visit, testing must continue as per standard of care in the Follow-up Phase. Test may be repeated as clinically indicated.

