		deemed necessary by the investigator, patients may also be observed after subsequent injections.			 Administration Medications for patients treated with daratumumab Lenalidomide 10 mg PO: Days 1 to 28 (continuously) of each 28-day cycle until confirmed PD, unacceptable toxicity, or until end of study treatment. If a patient experiences toxicity to lenalidomide, dose and/or schedule may be modified per institutional standard. After 3 cycles of maintenance therapy, if well tolerated, the lenalidomide dose may be increased to 15 mg daily, at the discretion of the investigator. The start of each cycle may occur ±3 days of the schedule day to accommodate the schedule of the site or patient. Day 1 of subsequent cycles should be adjusted accordingly to maintain the intended cycle duration. Any delays ≥4 days of the schedule day will need to be discussed with the sponsor.

				STUDY PHA	SES/VISI	TS ^a	
	PROCEDURE		SCREENING	Maintenance (Cycles 1–36)	ЕОТ	Follow-up (from the date of last study treatment until the end of study)	NOTES
	PROs						
	EORTC QLQ-C30, EORT EQ-5D-5L	At C1D1, and at the end of 6, 12, 24, and 36 months of treatment, (ie, C1D1, C7D1, C13D1, C25D1 and EOT). PROs should be administered at specified timepoints even after patient discontinues the study treatment.		PROs must be completed prior to conducting any other study-specific procedures. PROs should be completed at EOT if the patient discontinues early.			
	DISEASE EVALUATIONS						
	LABORATORY EVALUATION	S (TESTS TO BE CONDUC	TED AT THE CEN	TRAL LABORATORY)			
	IMWG Response Evaluat Assessment	ion per Investigator	х	D1 of every 3 rd cycle (ie, every 3 months) beginning with C1D1, during the first Year (ie, C1D1, C3D1, C6D1, C9D1, C12D1), followed by every 6 th cycle (ie, C18D1, C24D1, C30D1, C36D1) during Year 2 and Year 3	х	Every 6 months	IWMG Response Assessments during the Follow-up visits will be done for participants who have completed study treatment (36 cycles) or who have prematurely discontinued study treatment (due to reasons other than progressive disease). These assessments are to be performed based on local efficacy laboratory results. Assessments can stop after confirmation of Progressive Disease by the investigator. Determination of progressive disease, as well as other response assessments are to follow the IMWG criteria for assessment of progressive disease and disease response, as outlined in Table 7.
	β2-microglobulin and LDI	Н	X	-	Х	-	-

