3.2. Study Design Rationale

3.2.1. Overall Rationale for Study Design

Multiple myeloma, a malignant clonal disorder of plasma cells, is characterized by uncontrolled and progressive proliferation. Patients with multiple myeloma can produce a monoclonal paraprotein, otherwise known as a myeloma protein (M-protein), as well as a monoclonal free light chain (FLC), which is a fragment of immunoglobulin that is non-functional. The proliferation of myeloma cells causes displacement of the normal bone marrow. Normal immunoglobulin levels are compromised, leading to susceptibility to infections. Other frequently reported sequelae of multiple myeloma include hypercalcemia, renal insufficiency or failure, anemia, and neurological complications. According to data from the National Cancer Institute, Surveillance, Epidemiology, and End Results Program in 2018, multiple myeloma accounted for 1.8% of all new cancer cases and 2.1% of all cancer deaths. In addition, there were approximately 30,770 new cases of multiple myeloma with approximately 12,770 deaths due to this disease in 2018. Based on data from 2008 to 2014, the 5-year survival rate is 50.7%.

Treatment choices for multiple myeloma have advanced in recent years and vary with age, performance status, comorbidity, aggressiveness of the disease, and related prognostic factors. The standard treatment approach for newly diagnosed patients who are considered eligible for HDT includes multiple phases of therapy: induction, HDT and ASCT, and consolidation and maintenance.

The current standard of care in the maintenance setting includes treatment with lenalidomide after ASCT, based on randomized Phase 3 studies showing improvement in clinical outcomes with the use of maintenance therapy^{1,27} (see also the lenalidomide package insert). As of 2018, according to the National Cancer Comprehensive Network (NCCN), continuous treatment with lenalidomide is the preferred choice for maintenance treatment of multiple myeloma.¹⁸ For the most comprehensive nonclinical and clinical information on lenalidomide refer to the most current package insert.

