10. PATIENT COMPLETION/DISCONTINUATION OF TREATMENT(S)/ WITHDRAWAL FROM THE STUDY

10.1. Study Completion

A patient will be considered to have completed the study if he or she has finished all protocol-specified procedures, including 36 cycles of maintenance treatment, or, if he or she has completed all protocol-specified procedures before the end of the study and has not been lost to

follow-up, and has not withdrawn consent for study participation before the end of the study or has transitioned to commercial drug product.

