17.9. Study Completion/Termination

17.9.1. Study Completion/End of Study

The end of the study is defined as 36 months from the date of randomization of last patient. If a patient has died, the date and cause of death will be collected and documented in the eCRF. Patients benefiting from treatment with daratumumab and/or lenalidomide may continue receiving treatment after the end of the study treatment period of 36 months and after the end of the study, per the investigator's discretion. However, because the study specified treatment is for 36 months, the sponsor will not provide daratumumab and/or lenalidomide after the end of the study, unless required by local health regulatory authorities. The final data from the study site will be sent to the sponsor (or designee) after completion of the final patient assessment at that study site, in the time frame specified in the Clinical Trial Agreement.

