1.4. Sample Size Justification

Based on previous reports of MRD negativity rate in lenalidomide-treated myeloma patients, the anticipated MRD (at 10⁻⁵) negativity conversion rate is estimated to be 20% for patients treated with lenalidomide alone following post ASCT. Assuming a 20% absolute increase in MRD negativity rate (40% daratumumab plus lenalidomide versus 20% lenalidomide alone) by the end of 12-month maintenance treatment, a sample size of 214 patients (ie, 107 patients per treatment group at 1:1 randomization) will be needed to achieve at least 85% of power to detect such a treatment difference at a 2-sided alpha of 0.05 using continuity corrected chi-squared test.

Disease assessments for each patient will continue until 36 months from the date of randomization of the last patient. It is anticipated that this will yield 64 PFS events and provide approximately 79% power to detect a 50% reduction in the risk of progression or death (HR=0.50, translating to an improvement in median PFS from 60 months to 120 months) with a log-rank test at a 2-sided alpha of 0.05 with an accrual period of 1 year. One interim analysis using Obrien-Fleming alpha spending function is planned at the time of primary endpoint analysis when approximately 32 events are anticipated.

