7.1.2. Analysis Methods

Analysis of PRO data will be performed on the FAS. For subjects with multiple records at the same visit, the closest one to the scheduled visit date will be selected for analysis. Compliance rates for completion of EORTC QLQ-C30, EORTC QLQ-MY20, and EQ-5D-5L at each time point will be generated based on number of received and expected. Compliance is defined as the actual number of assessments received for a visit divided by the expected number of assessments for that visit, the expected number of assessments per visit will be determined by subject-level study completion status.

The PRO endpoints are secondary and not part of the statistical hierarchy. Type 1 error control will not be applied to PRO data.

Key PRO endpoints

- EORTC-QLQ-C30 GHS, Physical Functioning, Fatigue, Pain subscales
- EORTC QLQ-MY20 Disease symptoms scale
- EQ-5D-5L utility score and VAS

Descriptive statistics (n, mean, standard deviation, median, and range) at each time point and the change from baseline will be summarized by treatment group. Line plots of mean change from baseline, with standard error, over time will be displayed by treatment group.

A mixed effects model with repeated measures analysis will be conducted estimating change from baseline at each time point between two treatments. FAS subjects who have a baseline value and at least one post-baseline value are included in the analysis. Change from baseline will be fitted to a mixed effects model including subjects as a random effect, and baseline value, treatment group, time in treatment cycles, treatment-by-time interaction, and randomization stratification factor as fixed effects. A mean change between 5 and 10 points on the 1 to 100 scales of the EORTC QLQ-C30 and EORTC QLQ-MY20 has been defined as noticeable by subjects and regarded as a significant change or a meaningful change (EORTC Quality of Life Group).

For the key PRO endpoints, time to worsening and time to improvement will be derived. A distribution-based method will be used to define improvement/worsening in scores, i.e., half standard deviation away from the mean score at baseline combining both treatment groups.

Time to improvement will be summarized by using descriptive statistics such as mean, standard deviation, median and range.

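### Does Protocol 10.1, by listing a move to commercial drug in its definition of study completion, cost the PFS analysis its late events?

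*SAP*

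**What the plan says.** **The PFS projection.** SAP 1.4, matched by Protocol 11.2, states: "Disease assessments for each patient will continue until 36 months from the date of randomization of the last patient". From this it anticipates 64 events and about 79% power for a hazard ratio of 0.50, with medians of 60 and 120 months.

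**The completion definition.** Protocol 10.1 gives two routes to completion, each requiring all protocol-specified procedures. The second closes with: "has not withdrawn consent for study participation before the end of the study or has transitioned to commercial drug product".

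**Follow-up after treatment.** The Protocol Synopsis (Overview of Study Design) says: "After the EOT visit, patients will continue to be followed until the end of the study, every 6 months". In the Time and Event Schedule, Part 1, the note to the IMWG response row says these assessments "will be done for participants who have completed study treatment (36 cycles) or who have prematurely discontinued study treatment" for reasons other than progression. That note and Protocol 9.3.1 let assessments stop once the investigator has confirmed progression, and both use local laboratory results after treatment.

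**Continued drug.** Under Protocol 17.9.1, patients who benefit "may continue receiving treatment after the end of the study treatment period of 36 months and after the end of the study". The pregnancy-test row of the schedule provides for the same situation: "For patients remaining on lenalidomide after the EOT visit, testing must continue as per standard of care in the Follow-up Phase".

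**Censoring.** SAP 5.3.1 and Table 4 determine progression by computer algorithm and censor event-free patients at the last disease assessment. They do not mention EOT, study completion or commercial supply.

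**The concern.** Treatment is capped at 36 cycles of 28 days, which is shorter than the follow-up behind the 64 events, so some of those events must be observed off study treatment. Many patients can be expected to stay on drug at that point: Protocol 3.2.1 notes that "continuous treatment with lenalidomide is the preferred choice for maintenance treatment of multiple myeloma". If moving to commercial supply meant the study was complete, a site might cancel the remaining visits, while another site following the schedule would keep them. Visits that were never held cannot be recovered at analysis.

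Completion status is also used elsewhere in the SAP. For questionnaire compliance in section 7.1.2, "the expected number of assessments per visit will be determined by subject-level study completion status".

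SAP version 2.0 (May 2024) predates Protocol Amendment 4 (August 2024), which spelled out the local-laboratory assessments after treatment. Three points are therefore not explicit in SAP 5.3.1:

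- whether local follow-up values enter the algorithm;
- whether continuing the assigned drugs from commercial supply counts as subsequent antimyeloma therapy;
- which visit schedule defines two or more consecutive missed evaluations.

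PFS is the only endpoint tested in sequence after MRD conversion, and its planned power is already below 80%. At stake are events and power. Nothing suggests a bias between arms.

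**Working it through.** **Inputs.** From SAP 1.4: 107 patients per arm, exponential medians of 60 and 120 months, accrual over 12 months (taken as uniform), follow-up T from 36 to 48 months, two-sided alpha 0.05. The documents give no loss rate, so zero is assumed. The hazards are λ = ln 2/60 = 0.01155 and ln 2/120 = 0.00578 per month.

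**1. The plan's own figure.** Expected events per arm = 107 × [1 − (e^(−36λ) − e^(−48λ))/(12λ)].

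- Lenalidomide: 107 × (1 − 0.6161) = 41.1
- Daratumumab plus lenalidomide: 107 × (1 − 0.7847) = 23.0
- Total: 64.1

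Power = Φ(√(d/4) × ln 2 − 1.96). With d = 64.1 this is 79.2%. The plan reproduces.

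**2. Position at EOT.** Thirty-six cycles plus the 30-day EOT visit is (36 × 28 + 30)/30.4375 = 34.1 months. Event-free patients then number 107e^(−34.1λ) = 72.2 and 87.9 by arm, about 160 of 214. If every assessment ended there, events would be 34.8 + 19.1 = 54.0 (rounded parts) and power 72.1%. Placing EOT at month 36 gives 36.4 + 20.1 = 56.5 and 74.1%.

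**3. The schedule followed as written.** With visits every 6 months after EOT, the last assessed time is EOT + 6 × floor((T − EOT)/6). With EOT at 34.1, 34%, 50% and 16% of patients reach 0, 1 and 2 follow-up visits. Mean assessed time is 39.0 months against a mean T of 42. Events are 38.7 + 21.6 = 60.3 and power 76.8%. EOT at month 36 also gives 60.3 events and 76.8%.

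**4. The part that could be due to 10.1.** The right comparison is step 3 against step 2, because the drop from 64.1 to 60.3 comes from visit spacing and occurs however 10.1 is read.

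| Share moving to commercial drug and no longer assessed (assumed) | EOT 34.1: events, power | EOT 36: events, power |
|---|---|---|
| 0% | 60.3, 76.8% | 60.3, 76.8% |
| 50% | 57.1, 74.5% | 58.4, 75.5% |
| 100% | 54.0, 72.1% | 56.5, 74.1% |

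The maximum loss is 60.3 − 54.0 = 6.3 events and 76.8 − 72.1 = 4.7 points, or 60.3 − 56.5 = 3.8 events and 76.8 − 74.1 = 2.7 points. At 50% it is 76.8 − 74.5 = 2.3 points or 76.8 − 75.5 = 1.3 points. These counts are somewhat low, because the calculation credits events only up to the last visit, whereas a recorded death that Table 4 does not censor counts on its own date.

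**5. The text.** The closing clause of 10.1 can be read in three ways: as a separate route to completion, as an alternative inside a route that still requires all procedures, or with the negative carried over (has neither withdrawn nor transitioned). None of them instructs a site to stop visits. Protocol 10.2.2 lists the reasons for withdrawal from the study, and a move to commercial drug is not among them. Protocol 10.2.1 sends patients who stop treatment early into follow-up. The schedule's IMWG note names patients who completed 36 cycles, the group in question.

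**6. The SAP points.**

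- *Data source.* SAP 2.7 gives central values precedence only where both central and local exist. SAP 5.4.1 applies the algorithm to response after as well as during treatment. Local follow-up values therefore enter naturally.
- *Commercial continuation.* Footnote a of the schedule ties a new line of therapy to adding other agents because of progression, relapse or toxicity. Continuing the assigned agents does not meet that.
- *Missed evaluations.* A follow-up visit can only be missed against the schedule then in force, which is six-monthly.
- *Censoring.* Table 4's last row is open-ended, and the default is the last disease assessment.

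**The case for a change.** The strongest opposing case is that 10.1 does contain the clause, no sentence reconciles it with the schedule, and the population is large: about 160 patients event-free at EOT, with 64.1 − 54.0 = 10.1 projected events after it. An analyst can repair SAP wording before database lock but cannot recreate a missed visit. A move to commercial drug before EOT would cost more. If assessment stopped at month 24 for an assumed 25% or 50% of patients, events would fall to 58.0 or 51.9 and power to 75.2% or 70.5% on the continuous-time calculation.

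Part of this stands. The clause is loosely drafted, and the three SAP points are inferred rather than stated. The rest does not carry. That a site would stop visits is an inference from a disposition label, against an explicit schedule row. No passage describes a move to commercial drug during the treatment phase, and early stoppers without progression are covered by the same follow-up row. Of the 10.1 late events, 64.1 − 60.3 = 3.8 fall outside the six-monthly visits on any reading, so they cannot be charged to 10.1. The use of completion status in SAP 7.1.2 concerns a questionnaire denominator, not disease visits.

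Restating the projection as about 60 events and 77% would bring no gain. The plan presents an approximate continuous-time figure, ignoring visit spacing is a usual planning simplification, and 60.3 is itself on the low side.

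**Conclusion.** No change to the plan follows. The clause in Protocol 10.1 is an ambiguous piece of disposition wording. A trial run to its own schedule collects the late PFS data, because the Synopsis, the schedule, Protocol 9.3.1 and Protocol 11.2 all keep event-free patients under assessment to progression or study end. The stated 64 events and approximately 79% power are correct on the plan's inputs.

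The loss that could be laid to the clause is hypothetical: at most 6.3 events and 4.7 power points (EOT at month 34.1), or 3.8 events and 2.7 points (EOT at month 36). Those limits assume exponential PFS, uniform accrual, no other losses, every event-free patient moving to commercial drug at EOT, and every site stopping. The documents give no share for such moves. Nothing points to a difference between arms, and MRD conversion at 12 months is untouched. The unstated SAP details have natural answers within the documents that an analyst would adopt.

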1.5. Randomization and Blinding

This is an open-label study. Patients will be assigned in a randomized manner in a 1:1 ratio to receive either 1800 mg daratumumab SC in combination with lenalidomide or lenalidomide alone as maintenance therapy. Randomization will be stratified by cytogenetic risk (standard risk/unknown versus high risk) at screening as determined by the investigator.

